2.3.1. Primary Efficacy Analysis Set

The primary efficacy analysis set for all efficacy outcomes is the ITT analysis set. Subjects will be analyzed according to the treatment randomized.

2.3.2. Secondary Efficacy Analysis Set

The PP analysis set will be used to assess the consistency with the primary efficacy analysis.

2.3.3. Safety Analysis Set

The primary safety analysis set for all safety outcomes is the safety analysis set. Subjects will be analyzed according to the actual treatment received.

2.4. Definition of Subgroups

Homogeneity of treatment effects, both in HR and direction, will be assessed in the following subgroups classified at baseline and not limited to the following subgroups:

- Age (< 65 vs ≥ 65 ; <75 vs ≥ 75 years)
- Sex (men vs women)
- Race (White vs others)
- Race (White, Black, Asian, others)

- Geographic region (North America, South America, Western Europe, Eastern Europe, other)
- CrCl (≥ 30 to < 50 , ≥ 50 to < 80 , ≥ 80 mL/min)
- Body Mass Index (< 25 , ≥ 25 to < 35 , ≥ 35 kg/m²)
- Admitting diagnosis (HF with reduced ejection fraction (LVEF $\leq 45\%$), acute respiratory insufficiency or acute exacerbation of COPD, acute ischemic stroke, acute infectious disease, and inflammatory diseases)
- History of diabetes (yes vs no)
- History of cancer (yes vs no)
- Baseline D-dimer level ($> 2xULN$ vs $\leq 2xULN$)
- Baseline aspirin use (yes vs no)
- Baseline thienopyridine use (yes vs no)
- Baseline proton pump inhibitor use (yes vs no)
- Duration of index hospitalization (3 to 6, 7 to 10, > 10 days)
- Duration of anticoagulation during index hospitalization (3 to 6, 7 to 10, > 10 days)
- LMWH or UFH during index hospitalization (LMWH vs UFH)
- Use of US approved thromboprophylaxis (ie UFH, enoxaparin and dalteparin) vs other
- Total modified IMPROVE risk factor score (2, 3, ≥ 4)

3. INTERIM ANALYSIS AND DATA MONITORING COMMITTEE REVIEW

An interim analysis for futility will be conducted when approximately 50% of subjects with adjudicated primary efficacy outcome have been observed (about 50% of the expected total number of events based on the actual observed blinded pooled event rate even if this event rate is lower than the assumed rate).

There will be no alpha adjustment to the final analysis. The IDMC will review results of the planned interim analysis and make a recommendation whether the study should be continued as planned, modified, or terminated prematurely due to futility or safety.

The study may be stopped early for futility when it would be unlikely to establish superiority on the primary efficacy outcome and/or a positive benefit over risk of rivaroxaban compared with placebo, if the study were to run to completion. The IDMC are encouraged to make a judgment for early stopping for futility when any one of 3 conditions below meets:

- Estimated HR on the primary efficacy outcome is 1.0 or higher based on the interim analysis. (Refer to [Table 2](#) below for the corresponding conditional power)
- Observed primary efficacy outcome incidence rate by Day 45 in placebo at IA is too low that findings are not likely clinically meaningful
- Observed incidence rate of major bleeding on-treatment in rivaroxaban at IA is high enough that the overall benefit-risk profile would be unlikely to be positive at the final analysis as discussed in section 7

Table 2: Conditional Power (CP) Based on the Assumption of the Various Underlying RRRs in the Remaining Study.

Estimated HR=1 at IA 90% CI: (0.69, 1.44) 70% CI: (0.79, 1.26) 50% CI: (0.86, 1.16)	RRR in the Remaining Study	CP
	40%	32%
30%	12%	
20%	4%	
10%	1%	
0%	0.3%	

4. SUBJECT INFORMATION

4.1. Demographics and Baseline Characteristics

Descriptive statistics by treatment group will be provided for the following baseline demographics and disease characteristics, and not limited to the following baseline demographics and disease characteristics:

- Age
- Sex
- Race
- Geographic region
- CrCl
- Body Mass Index

- Admitting diagnosis (HF with reduced ejection fraction, acute respiratory insufficiency or acute exacerbation of COPD, acute ischemic stroke, acute infectious disease, and inflammatory diseases)
- History of diabetes
- History of cancer
- Baseline aspirin use
- Baseline thienopyridine use
- Baseline proton pump inhibitor use
- Duration of index hospitalization
- Duration of anticoagulation during index hospitalization
- LMWH or UFH during index hospitalization
- Use of US approved thromboprophylaxis (ie UFH, enoxaparin and dalteparin) vs other
- Total modified IMPROVE risk factor score
- Baseline D-dimer level ($> 2xULN$ vs $\leq 2xULN$)

4.2. Disposition Information

A subject will be considered a completer of the double-blind treatment if his/her last dose is at least at Day 45, at death date, or at primary efficacy outcome date. The number of non-completers of the double-blinded treatment and the reason for discontinuation will be summarized by treatment group. The distribution of time from the randomization to the last dose date will be shown by Kaplan-Meier plot.

The primary objective of this study will be addressed by primary efficacy outcome up to Day 45. Therefore, a subject will be considered a non-completer of the study if the subject's last outcome-evaluation date is before Day 45 date and the subject doesn't have a primary efficacy outcome or death before Day 45. The number of non-completers of the study and the reason for discontinuation will be summarized by treatment group. The distribution of time from the randomization to the last outcome-evaluation date will be shown by Kaplan-Meier plot.

A diagram similar to CONSORT Statement 2010 Flow Diagram¹ (Schulz et al, 2010) will be provided. A template of the diagram can be found in [Attachment 1](#).

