6. DOSAGE AND ADMINISTRATION

Treatment groups in this study are rivaroxaban and placebo. Subjects will be randomly assigned in a 1:1 ratio to receive rivaroxaban 10 mg daily (7.5mg daily in subjects with CrCl of ≥ 30 and

<50 mL/min) or matching placebo daily. Randomization will be stratified by subjects with CrCl \geq 30 and <50 mL/min versus subjects with CrCl \geq 50 mL/min and by country. The dose of study drug will not be adjusted in the event of change in CrCl between the 2 strata during the course of the study.

The first dose of study drug should be administered no later than the day after the subject leaves the hospital and as soon after randomization as possible. The date and time of the first dose of study drug and the last dose of LMWH or UFH should be recorded as accurately as possible. The first dose of study drug should not be delayed to allow administration under supervision. All subjects should take study drug (rivaroxaban or placebo) daily with or without food at approximately the same time each day, and discontinue study drug after they take a dose on Day 45. **Regardless of the day on which the Day 45 Visit occurs, no study drug may be taken after Day 45.**

A missed dose should be taken as soon as possible (up to 8 hours prior to the next scheduled dose), and the next scheduled dose should be taken at the regular time.

After the subject takes a dose of study drug on Day 45, the subject should discontinue study drug and complete the Day 45 (+4d) visit (refer to [TIME AND EVENTS SCHEDULE](#)). **Regardless of the day on which the Day 45 Visit occurs, no study drug may be taken after Day 45.** Throughout the study, study drug will be dispensed at appropriate intervals (see the [TIME AND EVENTS SCHEDULE](#)) to ensure that subjects have adequate quantities of study drug between study visits. In addition, study site personnel will instruct subjects on how to store study drug for at-home use as indicated for this protocol. The storage recommendation for rivaroxaban or placebo is at room temperature (approximately 15° to 30°C).

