2.1. Definition of Trial Dates

Trial reference start date: the date of randomization of the subject.

Trial reference end date: the date of the last trial-related procedure for the subject and is defined as the maximum of the following dates:

- Dates of all study-related visits (including scheduled or unscheduled visits)
- Dates of all study-related procedures, findings and events, including, but not limited to, adverse events, concomitant medications, disposition, clinical laboratories, vital signs, death

First dose date: the date on which the first dose of study drug is taken by the subject. If missing or incomplete for a subject who takes study drug, the first dose date is set to the earliest logically possible date on or after randomization. More specifically, the first dose date is defined as the maximum of the randomization date and the first day of the month if only day is missing, and is defined as the randomization date if day and month are missing.

Last dose date: the date on which the last dose of study drug is taken by the subject. If missing or incomplete for a subject who takes study drug, the last dose date is in general set to the latest logically possible date on or after the first dose date.

To ensure consistency with other data of the trial, more specifically, the above date will be further

- capped by (that is, taking the minimum with) Day 45 date, death date, trial reference end date, and the upper bound of the logically possible range if partial date is available, and
- further bounded below by (that is, taking the maximum with) the (imputed) first dose date, any complete temporary drug stop and re-start date, or the lower bound of the logically possible range.

Upper bound of the logically possible range is defined as the last day of the month if only day is missing and is defined as the last day of the following month after randomization if day and month are missing. Lower bound of the logically possible range is defined the maximum of the randomization date and the first day of the month if only day is missing and is defined as the randomization date if day and month are missing.

Last outcome-evaluation date: the date of last study visit (clinic/phone) while the subject is alive during which the outcome status is ascertained.

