2.3. Analysis set and Analysis Phase

Each analysis involves the following 2 aspects: 1) analysis set, specifying the subjects to be included; and 2) analysis phase, specifying the time window within which data will be included.

Key analysis sets and analysis phases are defined below.

Analysis sets

- Intention-to-Treat (ITT) (as termed Full Analysis Set in the International Conference on Harmonisation [ICH] E9 guideline): This analysis set consists of all randomized subjects who have a signed valid informed consent.
- Per-Protocol (PP): This analysis set is a subset of the ITT analysis set.

Subjects with the key protocol deviations will be excluded from the PP analysis set. The categories and terms of the key protocol deviations will include the following:

- Did not meet the following inclusion or met the following exclusion criteria;
 - INT-2, INT-3, INT-4: subject with index hospitalization > 14 days, inclusion criteria 1, 2, 4, 6, exclusion criteria 10, 11, 14, 22, 24, 27
 - INT-6, INT-7: inclusion criteria 1.2, 2.2, 4.3, 6.1, exclusion criteria 10.2, 11.1, 14.1, 22.2, 24.2 without c
- Did not take any assigned study drug or took wrong study drug
- Did not discontinue study drug permanently according to the protocol (The subject becomes pregnant, develops any condition which requires permanent anticoagulation, has a fall in CrCl to below 20 mL/min during the study, or has a hemorrhagic stroke or intracranial bleeding)
- Had been taking prohibited concomitant therapies as specified in the protocol
 - INT-2: 2, 3,
 - INT-3, INT-4: 2, 3, 4, 6, 7, 8
 - INT-6, INT-7: 2.2, 3.2, 4.1, 7.1 without c and i

- Safety: This analysis set is a subset of the ITT analysis set, consisting of subjects who receive at least one dose of study drug.

Analysis phases

- Up-to-Day-45: This analysis phase includes all data from randomization to Day 45 (inclusive).

For time to event analyses, subjects who do not have events to be analyzed on or before Day 45 will be censored on Day 45 or the last outcome-evaluation date whichever occurs first.

- On-Treatment: This analysis phase includes all data from randomization to 2 days after the last dose of the study drug (inclusive).

For time to event analyses, subjects who do not have events to be analyzed during this phase will be censored on the last dose + 2 or the last outcome-evaluation date whichever occurs first.

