The following sensitivity analyses of the primary efficacy outcome will be conducted to assess the robustness of the conclusion from primary efficacy analysis: a) stratified Cox model as in the primary efficacy analysis but additionally stratified by region, b) stratified Cox model as in the primary efficacy analysis but based on the per-protocol analysis set and on-treatment analysis phase. The additional sensitivity analyses of the primary efficacy outcome may be necessary to exclude subjects (e.g., significant quality issues, GCP violations, data integrity issues, regulatory agency commitment). Additional post-hoc analyses may be conducted to investigate unexpected

results. Off-treatment primary efficacy outcome events, defined by the events from the 3 days after the last dose date, will be summarized by treatment groups.

Extensive efforts will be made to collect complete event and vital status data for all subjects randomized in this study. The amount of unavoidable missing follow-up in this study with relatively short treatment duration of 45 days is not expected to influence the conclusion from the efficacy analyses. To illustrate the extent of missingness for the primary efficacy outcome, the numbers of subjects with missing follow-up and the percentages of total missing follow-up time out of total supposed follow-up time will be summarized. A non-completer of the study will be considered as a missing follow-up subject. Missing follow-up time will be calculated by Day 45 date - last outcome-evaluation date for a missing follow-up subject. For a subject, supposed follow-up time will be calculated by minimum of [Day 45 date, death date, first primary efficacy event date] - randomization date +1. Sensitivity analyses will be conducted to estimate any additional events from the rivaroxaban and placebo group during the missing follow-up time that are needed to overturn a superiority conclusion from the primary efficacy analysis. Similar sensitivity analyses may be conducted for each component of the primary efficacy outcome.

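### The treatment-completer rule in SAP 4.2 has no one-day allowance, so an adherent subject whose death or primary event precedes that day's tablet, with no later dose, is tabulated as a non-completer

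*SAP*

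**What the plan says.** SAP 4.2 makes a subject a completer of double-blind treatment if the "last dose is at least at Day 45, at death date, or at primary efficacy outcome date". Everyone else is a non-completer, and the result is reported by arm: "The number of non-completers of the double-blinded treatment and the reason for discontinuation will be summarized by treatment group".

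SAP 2.1 defines the last dose date as "the date on which the last dose of study drug is taken by the subject". If that date is missing or incomplete, "the last dose date is in general set to the latest logically possible date on or after the first dose date", subject to caps that include Day 45 and the death date.

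Protocol section 6 has subjects take study drug "daily with or without food at approximately the same time each day". No clock time is fixed.

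Two other SAP rules are more lenient around the same day. The on-treatment phase in SAP 2.3 runs to two days after the last dose, and SAP 5.2.2 accordingly counts off-treatment primary events as those "defined by the events from the 3 days after the last dose date". The study-completer rule, also in SAP 4.2, makes a subject a non-completer only if outcome evaluation ended before Day 45 and "the subject doesn't have a primary efficacy outcome or death before Day 45". It sets no condition on a dose.

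**The concern.** Death and the primary outcome are named as completion points so that a subject whose treatment ends because of one of them is not counted as having failed to complete. With one tablet a day and calendar dates, the rule achieves this only when a tablet was taken on the event date or later. If a pulmonary embolism occurs in the morning and the tablet is due in the evening, the last dose is dated the day before and the subject fails the rule.

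The Protocol makes this pattern plausible. Section 9.1.3 asks subjects with symptoms to contact the site before their next dose. Section 9.2.2 allows interruption or discontinuation for a suspected event. Section 10.2.3 gives VTE as an example of a condition leading to permanent discontinuation.

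At stake is a planned by-arm table that readers use to judge adherence. Because the trigger is the outcome itself, the arm with more events gains more non-completers.

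**Working it through.** **Inputs.** From SAP 1.4: hazard ratio 0.60, 90% power, two-sided 0.05, placebo rate 2.5%, about 8,000 subjects randomized 1:1, target 161 events. Assumed, because the documents do not give it: q, the share of primary events that precede that day's tablet, taken as equal in both arms.

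**The plan's own figure.** Schoenfeld's formula gives 4 × (1.960 + 1.282)² / (ln 0.60)² = 161 events (162 if rounded up), and 161 events give power 0.8999. With rates of 2.5% and 0.6 × 2.5% = 1.5%, the mean is 2.0% and N = 161 / 0.020 = 8,050. The plan's 161 and approximately 8,000 are reproduced.

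**The rule.** Completer if last dose date ≥ the earliest of Day 45, death date and primary event date.

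| Case | SAP 4.2 | SAP 2.3 |
|---|---|---|
| Primary event Day 20, last dose Day 19 | non-completer | on-treatment (19 + 2 = 21) |
| Primary event Day 20, last dose Day 20 | completer | on-treatment |
| Primary event Day 20, last dose Day 21 | completer | on-treatment |
| Death Day 20, last dose Day 19 | non-completer | on-treatment |

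**Size at design rates.** Expected primary events are 4,000 × 0.025 = 100 on placebo and 4,000 × 0.015 = 60 on rivaroxaban. Added non-completers per arm = events × q, if all these subjects were on drug until the day before and took no later dose.

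| q | Placebo | Rivaroxaban | Gap (percentage points) |
|---|---|---|---|
| 0.25 | 25 (0.63%) | 15 (0.38%) | 0.25 |
| 0.50 | 50 (1.25%) | 30 (0.75%) | 0.50 |
| 0.75 | 75 (1.88%) | 45 (1.13%) | 0.75 |

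The ratio is 1 / 0.6 = 1.67 for any common q, and the gap is q × 1.0 point.

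**At the enlarged size.** If 161 events came from 12,000 subjects, the split would be 161 / 1.6 = 100.6 versus 60.4. At q = 0.50 that gives about 50 versus 30, or 0.84% versus 0.50% of 6,000 per arm.

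**Compliance (SAP 4.3).** Actual duration ends at the last dose if that is earlier than the event, while intended duration runs through the event or death date. With first dose on Day 1, last dose on Day 19, event on Day 20 and no interruptions, actual = 19 days, intended = 20 days, and compliance = 19 / 20 = 95% for a subject who missed no dose before the event.

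**The case against.** The strongest reply is that nothing inferential depends on this flag, and that is correct. The primary test uses the ITT set up to Day 45. The per-protocol exclusions in SAP 2.3 do not include treatment non-completion. The on-treatment phase uses last dose plus two days. The missing-follow-up analysis in SAP 5.2.2 uses the non-completer of the study, whose rule has no dose condition.

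Several stronger readings are tempting but not supported:

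- A reader might infer that every subject with an event needs a dose on that very day. The wording means on or after, so a later tablet following a non-fatal event qualifies. Only death requires a dose on the day itself.
- A reader might infer that every such death is miscounted. A missing or incomplete last dose date is imputed late, up to the death date, which can produce a completer. A partial event date is set early (SAP 5.1.2), which also favours completer status. The fault concerns recorded dates.
- A reader might call these false discontinuations. The SAP's term is non-completer. A subject who permanently stops drug because of a VTE has a real, documented discontinuation; the point is only that SAP 4.2 evidently means to credit that subject as a completer.
- A reader might add deaths from other causes and quote a larger total. Such deaths could add to either arm, but the documents give no rate for them.
- A reader might infer that the flow diagram is distorted. Its template content cannot be read here, and programming instructions sit in a separate Data Presentation Specifications document, so this cannot be checked.

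After all this the wording still gives the wrong answer for a fully adherent subject, and no allowance appears in SAP 4.2 or 4.3.

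**Conclusion.** The rule is wrong as written, but the consequence is minor and descriptive. It adds non-completers in proportion to events. At design rates, primary events alone add 25 versus 15 to 75 versus 45 (placebo versus rivaroxaban) for q from 0.25 to 0.75, a gap of 0.25 to 0.75 percentage points.

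This rests on an assumed q common to both arms and on the design hazard ratio. For a given q the counts are upper figures for primary events: some subjects will already have stopped, and some will take a later dose. Amendment INT-7 also reports a pooled event rate below expectation, and randomization may stop short of 161 events, so the percentages and possibly the counts would be lower still.

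The disposition summary and the compliance rate are affected. The primary, per-protocol, on-treatment and missing-follow-up analyses are not.

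**What to change.** In SAP 4.2, define a completer of double-blind treatment as a subject with *last dose on or after Day 45, or on or after the day before the date of death or first primary efficacy outcome*.

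In SAP 4.3, apply the same one-day allowance. One way is to end both the actual and the intended duration no later than the day before death or the first primary event, and no earlier than the first dose date. The Day 20 example then gives 19 / 19 = 100%, whether or not a tablet was taken on Day 20. Both durations must be cut, or a subject dosed on the day of death would exceed 100%.

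The cost is a few words in two sections and a small program change, with no effect on alpha, power or data collection. The downside is that a few subjects who stopped for another reason exactly one day before the event would count as completers. Using the SAP's two-day on-treatment window instead would also remove the artefact, but would admit more such subjects; one day is enough for once-daily dosing.

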10. SUBJECT COMPLETION/WITHDRAWAL

10.1. Completion

The total duration for a subject who completes the study after randomization is expected to be 75 days.

All feasible efforts and measures will be made to collect complete vital status and other outcome data from randomization to the Day 75 ($\pm 5d$) visit for each subject randomized in this study, regardless of compliance with study drug or visits. For subjects who are lost to follow-up or withdraw consent from the study, efforts will be made to obtain their vital status and other outcomes from permitted sources.

It is important to note that withdrawal of consent does not withdraw permission to collect vital status and other outcomes. Withdrawal of permission to collect vital status and other outcomes must be made separately. In cases where subjects indicate they do not want to “continue”, investigators must determine whether this refers to discontinuation of study treatment (the most common expected scenario), unwillingness to attend follow-up visits, unwillingness to have telephone contact, unwillingness to have any contact with study personnel, or unwillingness to allow contact with a third party (eg, family member, doctor). In all cases, every effort must be made to continue to follow the subject, and vital status and other outcomes must be determined for all randomized subjects.

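### SAP 4.2 omits Day 45 from the rule that exempts subjects with an event or death from study non-completer status, so a few Day 45 deaths are recorded as missing follow-up (minor)

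*SAP*

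**What the plan says.** SAP 4.2 sets two conditions for a study non-completer: the "last outcome-evaluation date is before Day 45 date", and the subject does not "have a primary efficacy outcome or death before Day 45". It gives its reason for working to Day 45: "The primary objective of this study will be addressed by primary efficacy outcome up to Day 45".

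SAP 2.1 defines the last outcome-evaluation date as the last clinic or phone visit, with the subject alive, at which outcome status was established.

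SAP 2.3 runs the Up-to-Day-45 phase through Day 45 inclusive. Its censoring rule is that "subjects who do not have events to be analyzed on or before Day 45 will be censored on Day 45 or the last outcome-evaluation date". The earlier of these two dates applies.

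SAP 5.2.2 carries the SAP 4.2 flag into the missing-data work: "A non-completer of the study will be considered as a missing follow-up subject". Missing time for such a subject is the Day 45 date minus the last outcome-evaluation date. Supposed follow-up ends at the earliest of Day 45, death and the first primary event. A sensitivity analysis then asks how many additional events in the missing time would overturn a superiority conclusion. It adds: "Similar sensitivity analyses may be conducted for each component of the primary efficacy outcome".

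**The concern.** The completeness rule and the analysis window differ by one day. A subject can be a counted primary event, or a known death, on Day 45 and at the same time be listed as having missing follow-up. That affects the non-completer count by arm, the missing-time percentage and the follow-up time that enters the sensitivity analysis.

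A second, conditional issue concerns VTE-related death, which is a component of the primary composite and the first secondary outcome in the testing hierarchy. Under SAP 4.2 any primary outcome, including a non-fatal DVT or PE, makes the subject complete. That suits a time-to-first-event composite. It does not suit VTE-related death, for which a subject remains at risk after a non-fatal VTE. SAP 5.2.2 allows the sensitivity analysis to be repeated by component but defines no other flag.

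**Working it through.** **The plan's own figure, used here only for scale.** Schoenfeld's formula with HR 0.60, two-sided alpha 0.05 and 90% power gives 4 × (1.960 + 1.282)² / (ln 0.60)² = 161.07, which reproduces the target of 161 in SAP 1.4. This point does not dispute it.

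**The rules applied to test subjects.** The current rule is SAP 4.2, with missing time as in SAP 5.2.2. The second rule changes only the wording to *on or before Day 45*. The third is a flag for VTE-related death, under which only death or evaluation to Day 45 ends follow-up.

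| Subject | Current rule | On or before Day 45 | Flag for VTE-related death |
|---|---|---|---|
| Dies Day 44, last visit Day 21 | complete, 0 days | complete, 0 | complete, 0 |
| Dies Day 45, last visit Day 21 | non-completer, 45 − 21 = 24 days | complete, 0 | complete, 0 |
| VTE Day 45 known only from records, last visit Day 21 | non-completer, 24 | complete, 0 | non-completer, 24 |
| VTE Day 45, visit Day 47 | complete, 0 | complete, 0 | complete, 0 |
| No event, lost after Day 21 | non-completer, 24 | non-completer, 24 | non-completer, 24 |
| Non-fatal VTE Day 10, last visit Day 12 | complete, 0 | complete, 0 | non-completer, 45 − 12 = 33 |

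Row 2 is the error: row 1 differs by one day and gives the opposite result. Row 4 shows why most Day 45 VTEs are unaffected. The Day 45 visit window is −0/+4 days (Protocol 9.1.3), and any later study contact by clinic or phone also counts. Row 6 is the component issue.

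**Size of the Day 45 error.** The documents give neither a mortality rate nor a dropout rate, so these are assumptions.
- Deaths: if 1% to 2% of 8,000 to 12,000 subjects die, spread evenly over 45 days, Day 45 deaths number from 80/45 = 1.8 to 240/45 = 5.3, or about 2 to 5. A subject evaluated alive on Day 45 itself before dying is not misclassified.
- Primary events: 161/45 = 3.6 would fall on Day 45. This is a ceiling, because only those with no evaluation on or after Day 45 are misclassified.
- Days per subject: the Day 21 window is −3/+7, that is Day 18 to Day 28, so a last visit there gives 45 − 28 = 17 to 45 − 18 = 27 false missing days.
- Share of follow-up: take 2% mortality, every Day 45 primary event unseen afterwards, and 27 days each. With 8,000 subjects this is (160/45 + 161/45) × 27 = 193 days out of 45 × 8,000 = 360,000, or 0.05%. With 12,000 it is (240/45 + 161/45) × 27 = 241 out of 540,000, or 0.04%. Both sums count VTE-related deaths twice, so they overstate.

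**Size of the component issue.** If 1% to 10% of at most 161 subjects with a primary event are lost after a non-fatal VTE (assumption), that is 161 × 0.01 = 1.6 to 161 × 0.10 = 16.1, or about 2 to 16 subjects. The 161 is itself a ceiling, since it includes fatal events.

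**The case against.** The strongest reply is that nothing inferential depends on this. A Day 45 event enters the primary Cox model under SAP 2.3 whatever the SAP 4.2 flag says. The slip makes the primary outcome look slightly less complete than it is, so it does not flatter the trial. Ending follow-up at a first VTE is right for the stated purpose, because SAP 5.2.2 limits the missingness summary to the primary outcome. Censoring in SAP 2.3 is specific to the event being analysed, so a subject lost after a DVT is still censored correctly for VTE-related death and for all-cause mortality. All of this stands, and it is why the point is minor. It does not remove the contradiction between the two Day 45 rules, or the absence of a suitable flag for the optional component analysis.

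A reader might infer more than the documents support:
- *That losses between Day 46 and Day 75 are hidden.* Protocol 10.1 says "The total duration for a subject who completes the study after randomization is expected to be 75 days", and the SAP's label of study non-completer fits that poorly. But the Day 45 cut is deliberate and its reason is stated. The planned Kaplan-Meier plot of time to last outcome evaluation is not truncated at Day 45. Protocol 17.4 requires withdrawal reasons to be source-documented.
- *That the CONSORT diagram rests on this flag.* SAP 4.2 does not tie the two together, the template has no visible content, and table mock-ups are in a separate document.
- *That the sensitivity analysis would add an event to someone who already has one.* SAP 5.2.2 does not say how additional events are allocated.
- *That the component analysis covers all-cause mortality.* It is not a component of the primary outcome; only the general option in SAP 5.3.2 to apply other primary-outcome analyses to secondary outcomes could reach it.

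**Conclusion.** The concern holds as a minor inconsistency. SAP 4.2 wrongly classes as non-completers subjects who die on Day 45 without an evaluation that day, and the rare subject with a Day 45 VTE and no later evaluation. Under the assumptions shown, that is about 2 to 5 deaths plus at most 3.6 VTE events, and well under 0.1% of subject-days. Only the disposition count, the missing-time summary and the missing follow-up sensitivity analysis are affected. The primary test, alpha, power and event target do not change.

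The component issue is conditional. It arises only if the sensitivity analysis is run for VTE-related death with the existing flag, and it would then leave out about 2 to 16 subjects under an assumed 1% to 10% loss after VTE. Neither 3.6 nor 161 should be read as a number of misclassified subjects; both are ceilings.

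**What to change.** 1. In SAP 4.2, exempt subjects with a primary outcome or death *on or before Day 45*.
2. In SAP 5.2.2, state that if the sensitivity analysis is repeated for VTE-related death, follow-up is complete only at death or at an outcome evaluation on or after Day 45. Supposed follow-up for that outcome should then end at the earlier of Day 45 and death, and not at a first non-fatal VTE.
3. Optionally, report Day 75 completion by arm with reasons, separately from Day 45 completeness. This is a reporting addition and does not correct an error in the plan.

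The cost is one phrase, one sentence and one or two derived variables from data already collected. The first change slightly improves the reported completeness of the primary outcome; the second may slightly reduce it for VTE-related death.
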